We will assemble these measurements for each of the n subjects into the $n \times m$ matrix \mathbf{Y} . The design matrix \mathbf{X} is an $n \times p$ matrix, $\mathbf{X}_j(t) = [X_{j1}(t) \ X_{j2}(t) \ \dots \ X_{jp}(t)]$. In this case, the regression coefficients, which relate the independent to the dependent variables, are represented by the $p \times m$ matrix $\boldsymbol{\beta}$. Then, the multivariate linear regression model is given by: $\mathbf{Y} = \mathbf{X}\boldsymbol{\beta} + \boldsymbol{\varepsilon}$, where $\boldsymbol{\varepsilon}$ is the error matrix. The error terms corresponding to the m cognitive observations for the j th subject may be correlated. Likelihood ratio tests will be performed to assess the statistical significance of various components of the regression coefficient matrix $\boldsymbol{\beta}$, in order to determine which subsets of the independent variables can be used to predict variations in cognitive ability across subjects.

MCW Research Team and imaging facility: MCW is a national leader with a well-established model for basic and clinical translational research. Our MCW research group was the first to discover and develop R-fcMRI methodology in 1995 and has been at the forefront in developing R-fcMRI applications for nearly two decades. Our group has previously used R-fcMRI to describe changes in neural networks in a variety of diseases and conditions, including cocaine/heroin abuse, mTBI, pain, Alzheimer's disease, depression, and anesthesia, etc. Also, MCI imaging research center, has a team of imaging physicists and imaging processing scientists and the-state-of-the- art GE MR750 3T scanner to conduct the proposed studies.

Outcome measure and Impact: The proposed study will provide biomarkers for the functional pathophysiology of functional GI disorders, as well as other comorbidities that can lead to improved diagnostic and treatment options for these debilitating conditions and ultimately improve the long-term health and welfare of functional GI disorders.

G. RISK CATEGORY:

Nausea and IBS patients - 45 CFR 46.405: Research involving greater than minimal risk but presenting the prospect of direct benefit to the individual child subjects

Healthy controls in fMRI sub-study - 45 CFR 46.404: Research not involving greater than minimal risk to the children

H. RISKS AND THE PRECAUTIONS WHICH WILL BE TAKEN TO MINIMIZE RISK EXPOSURE

Gastric function tests:

Involved risks are minimal. Possible risks involve allergies to contents of formula or premade meal for GEBT; although these will be carefully screened for prior to enrollment there is a possibility of unknown allergies. Patients may experience some discomfort, nausea and possible vomiting with satiety drink test. However, patients are instructed to cease drinking at point of satiety so extreme symptoms should not be experienced.

Questionnaires:

Patient distress during questionnaire completion: If children become distressed during completion of study questionnaires, they are instructed in the consent and assent forms to inform the researchers or nurse. The researchers/nurse will then contact the primary investigator who will place a referral to a psychologist as necessary and as dictated by law (e.g., suspected child abuse/neglect) to ensure patient and family safety and to address psychosocial needs.

Patient/Parent report of clinically significant psychosocial or safety issues: Any child endorsing clinically significant psychological distress on questionnaire-reported screening measures will be referred to a psychologist. The PROMIS anxiety and global health scales will be scored by research coordinators within a week of completion. The raw score will be converted to a standardized T score where a T score of 50 represents the mean for a U.S. general pediatric population with a standard deviation of 10. Subjects scoring greater than 2 standard deviations below the mean will be reported to the PI. The PI will discuss the results with the family and provide them with a referral to a licensed clinical psychologist ([name]) as necessary.

Heart Rate Variability:

Participants will be asked in advance if they have a history of skin allergy to adhesives to avoid provoking any skin irritation or rash. However, some redness from the adhesive on the ECG surface electrodes may temporarily appear.

Neurostimulation:

Overall risks/ discomforts involved are very minimal – Rare (event rate 1% - < 5%)

Possible risks/discomforts may involve:

- a. Discomfort upon insertion of the electrodes for < 5 minutes - Rare (event rate 1% - < 5%)
- b. Discomfort at the lead placement site > 5 minutes – Rare (1 % - < 5%)
- c. Bleeding at the electrode site if the neurovascular bundle is penetrated - Rare (event rate 1% - < 5%)
- d. Localized discomfort if the electrodes should become dislodged during the wearing of the device - Rare (event rate 1% - < 5%)
- e. Localized dermatitis - Rare (event rate 1% - < 5%)
- f. Drop in blood pressure - Rare (event rate 1% - < 5%)
- g. Syncope (fainting) - Rare (event rate 1% - < 5%)

Adverse effects to supporting personnel

- a. Skin piercing with percutaneous needles - Rare (event rate 1 % - < 5%)

**In our recently completed randomized trial of auricular neurostimulation for functional abdominal pain (unpublished data), there were no significant or serious adverse events noted. Of 115 enrolled subjects, 10 reported side effects for following reasons, none of which were serious: ear discomfort n=6 (three active/three placebo device); adhesive allergy n=3 (one active/two placebo); syncope due to needle phobia n=1 (placebo).

fMRI sub-study

- 1) Interviews and surveys: In this case that the subject becomes tired they will be permitted to rest.
- 2) Magnetic Resonance (MRI) Studies: MRI studies are associated with the following risks and discomforts:

- a) An MRI machine acts like a large magnet. If the study subject has a pacemaker or any metal, such as an aneurysm clip, ear implant, or nerve stimulator in their body, they will not be allowed to have an MRI scan.
- b) If a piece of metal (such as a tool, keys, or watch) is released into the scanner room, study subject may be injured. This chance is minimized by careful screening and by having only trained technicians or assistants in the immediate area, which is otherwise restricted.
- c) Subjects will be required to wear ear protection to minimize noise injury in the scanner.
- d) If the child brings credit cards, other magnetic media, or fine electronics or devices (such as a watch) into the MRI scanner room, they may be damaged by the strong magnetic field. The risk is minimized by proper screening before entering the scanner room.

3) Pregnancy Related Risk: Pregnant women will not take part in this research study. The effects of a MRI scanner on an unborn baby are not known. All female participants past puberty will take a urine pregnancy test prior to participating in the fMRI scan.

4) Fathering a child: The effects of a MRI scanner on an unborn baby are not known. Participants should not father a baby while in this study.

5) Claustrophobia: If the subject experiences fear of being trapped in a narrow space the scan will be stopped. If the subject wishes to re-attempt the scan another appointment can be made.

There may be other risks and side effects that we cannot predict. If these should occur the participant should discuss them with the researcher and /or their regular doctor.

Safety Monitoring Plan

All procedures will be performed by trained professionals within the standard of care under continuous medical supervision in the hospital setting (research unit). Side effects will be inquired about and documented every week during the study and at the post-study follow-up visit. Daily nausea ratings will be filled out by patients so this will be carefully monitored. If any serious harm or discomfort is identified by the subjects or the study personnel, the treatment will be discontinued. Any patient with worsening or no improvement in symptoms during the study will be able to drop out at any time and receive standard of care medical therapy. The skin of the external ear will be carefully disinfected to avoid any infection risks. Subjects will undergo vital sign screening before enrollment and vital sign assessment before neurostimulator placement.

Safety Analysis Plan

There are no dangerous interventions related to this study, and the short study timeline allows for discontinuation of treatment when it is proven to be ineffective.

Completion of psychometric questionnaires may be associated with mild distress in some participants. Because the questionnaires include assessment of patient psychosocial functioning, clinically significant symptoms that the patient or parent were unaware of may be brought to light.

Patient distress during questionnaire completion: If children become distressed during completion of study questionnaires, they are instructed in the consent and assent forms to inform the researchers or nurse. The researchers/nurse will then contact the primary investigator who will place a referral to a psychologist as necessary and as dictated by law (e.g., suspected child abuse/neglect) to ensure patient and family safety and to address psychosocial needs.

Patient/Parent report of clinically significant psychosocial or safety issues: Any child endorsing clinically significant psychological distress on questionnaire-reported screening measures will be referred to a psychologist. Regarding psychological screeners, research assistants will score the PROMIS questionnaires within a week of completion. Any scores 2 or more standard deviations above mean will be reported to the PI. In turn, the PI will discuss the results with the family and provide them with a referral to a licensed clinical psychologist as necessary.

I. PROVISION FOR THE PROTECTION OF PRIVACY OF SUBJECTS AND TO MAINTAIN THE CONFIDENTIALITY OF DATA

All research projects that collect electronic data must use appropriate security measures to ensure that data is protected from theft or loss in order to prevent breaches of confidentiality. You must indicate what encryption tools (or why they are not necessary) from the options below. The IRB will not review this protocol unless you indicate the encryption tools being used to secure your research data. If you do not have encryption in place on your systems, please contact your Information Systems support to arrange for one of the encryptions options listed below.

The following encryption products employ cryptographic modules that the National Institute of Standards and Technology has certified as meeting FIPS 140-2 requirements. Children's Hospital and Health System endorsed the use of these products made to encrypt hard drives and removable media. All electronic research data must be encrypted using one or more of these products.

Please indicate which encryption tools you are using to secure your research data.

- Credent Mobile Guardian (RS, PD)
- GuardianEdge Hard Disk and GuardianEdge Removable Storage Encryption (HD, RS, PD)
- IronKey encrypted flash drives (RS)
- McAfee Endpoint Encryption (HD, RS)
- Microsoft Bitlocker (HD, RS when used with Windows 7 and FIPS compliant algorithms are enabled)
- PGP Whole Disk Encryption and PGP Portable (HD, RS)
- SafeNet Protect Disk and SafeNet Protect File (HD, RS)
- Seagate Secure Self-Encrypting Drives (HD when encryption option is enabled)
- Symantec Endpoint Encryption (HD, RS, PD)
- WinMagic SecureDoc encryption (HD) (for MCW owned computers)
- Other (add description)

Does not apply because:

- Data is de-identified – no PHI collected
- Data is stored on paper only
- Data is stored on CHW secured shared drives.
- Data is stored on MCW secured shared drives.

Key

HD = Hard Drive

RS = Removable Storage (USB flash drive, CD, etc.)

PD = Portable Device (iPod; iPhone; PDA, etc.)

Each subject will be assigned a unique identifying number which will be the only identifier listed on the questionnaires, GEBT and neurostimulator kits and all data collection forms. Each subject's identifying number and related electronic data will be kept on a secured, MCW password-protected database that provides access only to the PI and research staff. Only authorized research personnel will have access to the database. A separate secure database will have the subject identification number linked to the patient's name and info. The GEBT kits and neurostimulator devices will be shipped directly from the manufacturer (Key Electronics) to the GI office research coordinator who will label each package of 4 neurostimulator devices with a patient ID and serial number with a prepared sticker label. A subject folder will also be prepared and labeled with the same ID and kept together with the device package. The devices will be stored in a locked room in the division of gastroenterology. The kits will be transported by a research coordinator to the TRU on the day needed. The remaining kits will be stored in a locked room in the GI clinic, labeled with the patient's ID. Only research coordinators within the division of gastroenterology will have access to the storage room. To track use and

proper disposal of the devices, subjects will be asked to return the used device the following week (at time of the next stimulator placement or follow-up clinic visit if week 4). The doctor or research coordinator will record that device was returned and dispose it properly. The research coordinator will log this data every week on each subject as devices are returned.

J. PROVISIONS FOR MONITORING DATA TO ENSURE THE SAFETY OF SUBJECTS; AND ADDITIONAL SAFEGUARDS TO PROTECT THE RIGHTS AND WELFARE OF SUBJECTS WHO ARE LIKELY TO BE VULNERABLE

The PI will monitor the health of all patients in the study per standard clinical practice. The PI will monitor protocol adherence and supervise data collection, entry, and analysis.

K. ANTICIPATED BENEFITS ASSOCIATED WITH THE PROTOCOL TO HUMAN RESEARCH PARTICIPANTS AND SOCIETY

There are numerous, possible direct and long-term benefits to the subjects in this study. Our recently completed study of EAD in children with various functional abdominal pain disorders demonstrate improved pain, global well-being and functioning after only 3 weeks of therapy with effects sustained at 2 months follow-up (manuscript under review). Since it is well documented that functional disability and quality of life is worse in adolescents with functional pain disorders with concurrent nausea than in those without nausea,^{13,9} and as many subjects in the above trial were noted to have improvement in concurrent nausea, we postulate that some of the improvement in well-being and functioning may be due to reduction in nausea (along with pain). There is now also mechanistic data through heart rate variability studies before and after therapy (unpublished data), suggesting the EAD acts through peripheral vagal nerve stimulation effects. Given the known vagal pathways involved in nausea and vomiting, we anticipate a reduction in nausea in subjects suffering from chronic functional nausea. Our prior studies on functional nausea show a high prevalence of anxiety and co-morbid GI symptoms including bloating, fullness and discomfort.^{13,24} Based on our prior data, we therefore also anticipate that concurrent symptoms such as bloating, post-prandial fullness, and anxiety may improve. Of 104 subjects analyzed, there were no significant side effects reported other than mild ear discomfort (n=6; n=3 in active and n=3 in placebo arm), adhesive allergy (n=3), and one subject with syncope due to needle phobia (placebo arm). Adolescents suffering from functional GI disorders thus have the opportunity to benefit from a non-pharmacological and non-invasive therapy without the adverse effects of pharmacological agents. The results of this study may provide important insights to the medical field regarding a poorly characterized group of patients and the underlying mechanisms.

As an added incentive, all participants who complete the study will receive a \$75 check mailed to their address on file. Those who complete the fMRI portion will receive \$125. Subjects who do not complete all parts of the study, will still receive a prorated stipend of \$10 per each week of therapy they completed.

L. STOPPING POINTS THAT WOULD NOT ALLOW THE STUDY TO CONTINUE AS PROPOSED

Stopping points for the study include achieving adequate information on enough of the goal subjects, unanticipated adverse events, and inability to obtain enough data or patients/caregivers electing to discontinue the study.

Reporting Adverse Events and Unanticipated Problems

Expected adverse events that are not serious will be reported on the Continuing Review Progress Report. Continuing Review will be performed on a 12-month cycle, starting at time of protocol's initial approval. More frequent progress reports will be submitted at the request of the IRB.

Serious Adverse Events: The PI, within 24 hours, will report all serious adverse events occurring in any enrolled subjects to the IRB. Unexpected (but not serious) adverse events occurring in enrolled subjects which,

in the opinion of the PI, are possibly related to participation in the protocol will be reported by the PI within 5 working days to the IRB.

Unanticipated problems involving risks to subjects or others will be reported to the IRB within 24 hours.

M. IS THERE A DATA SAFETY MONITORING BOARD IN PLACE? WHO ARE IT'S MEMBERS? HOW OFTEN DO THEY MEET?

As this is a low risk protocol, no data safety monitoring board will be appointed unless requested.

N. DESCRIBE HOW THE CONSENT PROCESS WILL TAKE PLACE. INCLUDE A LIST OF APPROPRIATELY TRAINED PERSONNEL WHO WILL BE INVOLVED.

Written informed consent for participation will be obtained from the parents and children for their child's participation. Written assent will be obtained from youth 12 and 13 years of age using the CHW assent form. Patients ages 14 and above will sign the assent line on the consent form per CHW policy. Consent will be obtained by a study investigator or member of the research team at the patients' appointment in the GI Clinic. Volunteers' consent will allow for accessing information collected for program evaluation/clinical purposes. Participating children and parents will have the option of having the consent/assent document read aloud to them to facilitate understanding. Copies of signed consent/assent documents will be given to participants. When consent is given for a minor child to participate in a research study by one or both parents, and the child reaches the age of majority (18 years) the child will be re-consented as an adult to continue participation in the study. If age of majority is reached while the participant is active and continues to receive study interventions per the study protocol, he/she will be re-consented using the most current approved IRB informed consent document and HIPAA form. If age of majority is reached after all study interventions have been completed and the participant remains in the study for purposes of data collection for outcomes only a separate "Age of Majority" informed consent will be obtained.

O. PROCEDURES TO BE EMPLOYED IN ANALYZING DATA AND THE ANTICIPATED SIGNIFICANCE OF THE PROPOSED STUDY

Analyses will be conducted with SPSS and SAS software programs. Probability levels of $< .05$ will be used as cut offs for statistical significance.

The key significance of this study is the identification of a successful, non-invasive therapy for chronic nausea and to study the underlying brain connectivity that may be altered by this therapy. With this study, we hope to lay the foundation for the application of auricular neurostimulation for pediatric functional GI disorders by demonstrating effects on brain network. This is an innovative and novel treatment, which will enhance our knowledge on the brain-gut neural connectivity underlying functional disorders and ultimately improve patient care.

P. FINANCIAL RELATIONSHIPS

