Specific aim #1: Define functional nausea (FN) as an entity subdivided by measures of arousal, anxiety and gastric motor function.

Hypothesis: Adolescents with chronic nausea form subgroups based on clinical, physiologic and psychological parameters: 1) FN: characterized by high anxiety and emotional arousal, autonomic imbalance/low vagal tone and absence of major foregut dysmotility, 2) gastroparesis, and 3) poor gastric compliance. We will separate FN from other groups by clinical questionnaires, autonomic tests (heart rate variability) and gastric motility tests (gastric emptying, accommodation tests).

Specific aim #2: Demonstrate that resting state functional brain connectivity is different in female adolescents with FN compared to gender and age-matched healthy controls.

Hypothesis: Adolescents with FN will have altered rsFC between brain regions associated with emotional arousal neurocircuits (amygdala) and the top-down regulation of these by the prefrontal cortex. There will be decreased resting state functional connectivity between the ventromedial prefrontal cortex (vmPFC) and amygdala in adolescents with FN compared to healthy controls.

Specific aim #3: Demonstrate that four weeks of auricular neurostimulation improves nausea while strengthening the vagal tone and the abnormal resting state brain connectivity in female adolescents with FN compared to baseline and to more resemble that of healthy controls.

Hypothesis: 3a) Compared to baseline (pre-stimulation), there will be reduction in nausea and concurrent symptoms in the active compared to sham neurostimulation group after 4 weeks of therapy. 3b) Active neurostimulation therapy will increase vagal tone compared to baseline and also increase the rsFC between the vmPFC and amygdala in female adolescents with FN.

C. BACKGROUND, SIGNIFICANCE, AND RATIONALE

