One of the primary concerns in interpreting fMRI data obtained in children and in making comparisons across age groups involves the significant developmental changes in brain morphology that occur during childhood and adolescence. Although the majority of brain growth occurs prior to the age of 5 years, it has been estimated that approximately 5-8% of cerebral growth occurs between the age of 5 years and adolescence.⁴¹⁻⁴⁴ Furthermore, brain maturation proceeds at different rates in different regions of the brain. Concerns have been raised regarding the possible effects of these developmental changes on the process of spatial normalization, which involves transformation of images to a common stereotactic space based on an adult-derived template. The latter process is necessary in order to make direct voxel wise comparisons across subjects and subject groups. Recent studies do support the feasibility of making such comparisons within a common stereotactic space, suggesting that anatomical differences between the atlas transformed brain morphology of children (aged 7 to 8 years) and adults are minimal, relative to the level of resolution possible with current functional imaging and that would not result in spurious functional differences.^{45, 46} This study will include only adolescents who are at least 12 years of age, further minimizing any potential developmental effects.

Study Population

80-100 adolescents with chronic nausea and a subgroup of 15 patients with IBS as well as 15 healthy controls, between ages of 12-18 years, will be enrolled. All subjects will undergo gastric motor function and HRV testing at baseline followed by four weeks of auricular neurostimulation or sham therapy. By definition, all adolescents in this study will have no clear explanation for their symptoms after undergoing medical workup per standard of care.

Inclusion Criteria (Nausea and IBS Groups):

- Children aged 12 years to 18 years who provide written assent and whose parents provide written permission for participation

- English-speaking and able to verbalize their condition and concerns about nausea, pain and other symptoms
- Subjects will meet Rome IV criteria for functional nausea as determined by a pediatric gastroenterologist
- Subjects included in the IBS group will meet Rome IV criteria for Irritable Bowel Syndrome

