- Patients must have an intact external ear that is free of infection or severe dermatological conditions, have stable vital signs for their respective age, no history of seizures and no currently implanted electrical device
- Subjects included in the FN group include those who meet Rome IV criteria for functional nausea and have:
 - 1) autonomic imbalance with low vagal tone defined as baseline resting supine RMSSD value 2 or more standard deviations below the mean on HRV measurements, and
 - 2) normal gastric motor function (absence of gastroparesis or impaired accommodation). The gastric motor function and HRV tests will be compared to normative values obtained through a separate, ongoing, IRB-approved protocol (# 1030543-2)

Exclusion Criteria (Nausea and IBS Groups):

- Other pain-related diseases or somatization disorder
- Mental retardation or pervasive developmental disorder or epilepsy
- Psychosis
- Genetic or chromosomal disorders
- Pregnancy
- Subjects who admit to substance abuse during screening
- Patients with findings of peptic ulcer disease, H.pylori gastritis, celiac disease, inflammatory bowel disease, allergic disorders, or any chronic condition or medication that may cause nausea or pain
- Patients who are treated with opioids or who had any changes in their medical regimen in the past four weeks prior to study
- Patients with a history of allergy to adhesives
- Patients with a lactose intolerance

Study Design Overview

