- Subjects who have no previous disorders or history, symptoms or signs of gastrointestinal disorder, fibromyalgia, chronic fatigue syndrome, migraine, chronic dizziness while upright, PTSD, panic disorder, functional gastrointestinal disorders, constipation or fecal incontinence, diagnosis of postural tachycardia syndrome, diabetes, asthma, neuropathy
- Subjects who have not seen by a gastroenterologist within 2 years of enrollment at the discretion of the PI.
- Subjects who have no chronic gastroenterology complaint

fMRI Sub-study exclusion (All Groups):

- Currently receiving any medication that will strongly affect fMRI results
- Patients with pacemakers, metal clips used in previous surgery or other device which are not compatible with MRI scanning (for sub-study group only)
- Inability to lie still in the scanner (for sub-study group only)
- Claustrophobia or inability to lie still in the scanner (for sub-study group only)
- Orthodontic braces or permanent retainers (for sub-study group only)
- Patients who are unable to tolerate noise produced by the MRI

Visit 3: Following completion of the questionnaires, subjects who wish to do a mock scanning, will be scheduled for a 30-minute test fMRI session in the mock scanner. If the subject tolerates this, they will complete the fMRI scan. When fMRI scan is completed, subjects in the experimental group will have the neurostimulator placed (see section on placement details) by a study investigator who is a certified MD.

Post #1: Subjects in the fMRI sub-study (FN or IBS groups) will return to the scanner to complete their final fMRI scan on day 5 of last week of therapy, after removal of the EAD device.

E. TOTAL NUMBER OF HUMAN RESEARCH PARTICIPANTS PROPOSED FOR THIS STUDY AT THIS SITE AND GLOBALLY. WHAT ARE THESE NUMBERS BASED ON?

We aim to enroll 80-100 adolescents with chronic nausea for phenotyping with tests and clinical questionnaires followed by randomization to neurostimulation or sham therapy. A subset of 15 adolescent females and 15 age-matched females with IBS will enter a sub-study involving the same procedures as well as pre and post treatment fMRI scans. Baseline fMRI data will be compared to scans obtained in 15 healthy, age and gender matched healthy controls.

F. DRUGS OR PROCEDURES

Table 1.

| | Pre | Visit 1 | Visit 2 | Visit 3 | Visit 4-5 | Visit 6 | Post #1 | Post #2 |
|--|-----|---------|---------|----------------|-----------|----------------|---------|---------|

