Aim 3. *Hypothesis 3a): Four weeks of active neurostimulation will reduce nausea and concurrent symptoms from baseline compared to sham therapy as measured by weekly Nausea Severity Scale total score (primary outcome) after 4 weeks of therapy. Secondary outcomes include daily nausea (BARF) scores, and weekly nausea profile scores, upper GI symptoms (PAGI-SYM), abdominal pain (API), anxiety (SUDS, PROMIS and VSI), quality of life (PROMIS), disability (FDI) and co-morbid symptoms (CSI).* Another secondary efficacy variable will be the change in Nausea Severity Scale score after the second 4 weeks of therapy in a subset of subjects. We will compare pre and post total nausea, GI symptoms, anxiety, disability, quality of life and co-morbid symptom scores using a two-sided paired *t*-test at a Bonferroni corrected alpha of 0.05. Power: with ~40 in each group initially, allowing for 12% dropout based on our prior study, we will have ~35 subjects and 80% power to detect a difference of at least XX standard deviations (SD). We will similarly compare the other variables. Further we will use regression and regression trees with final value as the outcome and demographics, baseline values and overall symptoms as covariates. *Hypothesis 3b: Adolescents with FN will have reduced vagal tone as measured by HRV. Active neurostimulation therapy will elevate vagal tone compared to baseline and sham therapy, resembling that of healthy controls.* We will similarly analyze the change in vagal tone in nausea subjects. Further we will compare

the final vagal tone to healthy using a two sample t-test of equivalence where equivalence will be defined as within 20%. See fMRI analysis section for details on resting state fMRI analyses.

Longitudinal Continuous Variables

The efficacy parameters of longitudinal continuous variables such as nausea and pain will be analyzed using a mixed effects covariance pattern model to utilize all the data collected over time with consideration of the variance-covariance matrix of the repeated measures. This method allows a general unstructured variance-covariance matrix and allows patients to have incomplete data across scheduled time points. The method applied is also known as mixed-effects repeated measures analyses (MMRM).

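### Aim 3 and Hypothesis 3b name patients with FN, but the randomised comparison and the vagal-tone analysis cover all eligible functional-nausea patients, so the plan yields no estimate for FN

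*Combined protocol and SAP*

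**What the plan says.** **Population named.** Section B, Specific aim #3, places nausea, vagal tone and connectivity in one sentence: "four weeks of auricular neurostimulation improves nausea while strengthening the vagal tone and the abnormal resting state brain connectivity in female adolescents with FN". Of its two hypotheses, 3a says only that "there will be reduction in nausea and concurrent symptoms in the active compared to sham neurostimulation group after 4 weeks of therapy". Hypothesis 3b claims a rise in vagal tone and that stimulation will "increase the rsFC between the vmPFC and amygdala in female adolescents with FN". The Power section (Aim 3) restates 3b for adolescents with FN, without the sex limit.

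**What FN means.** Aim 1 makes FN one of three subgroups of chronic nausea, beside gastroparesis and poor gastric compliance: "We will separate FN from other groups by clinical questionnaires, autonomic tests (heart rate variability) and gastric motility tests". The inclusion list in section D defines the FN group as Rome IV functional nausea with supine RMSSD at least 2 SD below the mean and "normal gastric motor function (absence of gastroparesis or impaired accommodation").

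**Who is randomised.** The general inclusion criteria set an age range and no sex limit: "Children aged 12 years to 18 years who provide written assent and whose parents provide written permission for participation". Nausea patients must meet Rome IV functional nausea. Section E plans "80-100 adolescents with chronic nausea for phenotyping with tests and clinical questionnaires followed by randomization to neurostimulation or sham therapy". The EAD treatment protocol gives 40-50 patients an active device and 40-50 a sham, allocated 1:1 in blocks of 10 with no stratification. The female-only rule belongs to the fMRI sub-study, which scans 15 females classified as FN.

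**What is analysed.** The Power section counts "with ~40 in each group initially, allowing for 12% dropout based on our prior study, we will have ~35 subjects" and leaves the detectable difference as XX SD. The primary mixed model has treatment, visit, baseline and their interactions, with no FN or sex term. Vagal tone is to be analysed in nausea subjects.

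**The concern.** The aim and the 3b hypothesis make a claim about a subgroup, while every planned randomised analysis averages over a larger group. If the plan is followed exactly, the trial ends with one active-versus-sham estimate in all randomised nausea patients and none in FN. A positive result could then be written up as Aim 3 achieved, that is, as benefit in female FN, without that group having been examined. The vagal-tone hypothesis has the same problem: it is stated for patients selected for low vagal tone and would be answered in patients who mostly may not have it.

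With no FN analysis prespecified, an FN result added after unblinding would carry little weight. FN status is available in time to avoid this: HRV is taken at the Pre visit, gastric emptying at Visit 1 and the drink test at Visit 2, all before the first device at Visit 3.

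**Working it through.** **1. The populations side by side**

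| Element | Population |
|---|---|
| Aim 3 sentence | Female, FN |
| Hypothesis 3a (section B and Power section) | Active vs sham, no sex or FN limit |
| Hypothesis 3b, section B | Female FN |
| Hypothesis 3b, Power section | FN, both sexes |
| Vagal-tone analysis, Power section | Nausea subjects |
| Randomisation (sections D, E, F) | Rome IV functional nausea, both sexes |
| Primary model | All randomised, no FN or sex term |
| fMRI sub-study | Female FN, n = 15 |

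Hypothesis 3a, the randomisation and the primary model agree with each other. The Aim 3 sentence and 3b do not agree with the analyses meant to address them.

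The FN definition sits inside the inclusion list but is worded as membership of a group. Treating it as a condition for randomisation would conflict with section E, where the same 80-100 patients are phenotyped and then randomised. That gastroparesis and poor-compliance patients are randomised therefore follows from the absence of any such condition; the plan does not say so outright.

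**2. The plan's own figure**

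40 × (1 − 0.12) = 35.2, so ~35 per arm reproduces. It counts all randomised nausea patients. The XX SD cannot be checked. For a two-sample t-test at two-sided 0.05 and 80% power, 35 per arm detects 0.68 SD (normal approximation: (1.960 + 0.842) × √(2/35) = 0.67).

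**3. A floor for the FN share**

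The documents give no FN share. Section E draws the scanned patients as a subset of the study, and the imaging section says they are 15 females classified as FN. If that target is met, FN is at least 15/100 = 15% to 15/80 = 18.75% of those randomised. At the minimum, evaluable FN per arm is 15 × 0.88 / 2 = 6.6, about 7.

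**4. What the data could say about the named group**

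The shares below are assumptions, applied to 35 per arm. The half-width is 1.96 × √(2/n). For the treatment-by-FN difference it is 1.96 × √(2/n + 2/(35 − n)). Both are in SD units.

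| Share | n per arm | Detectable difference, 80% power | Power at 0.68 SD | 95% CI half-width in the subgroup | Half-width of interaction |
|---|---|---|---|---|---|
| 20% | 7 | 1.63 | 22% | 1.05 | 1.17 |
| 30% | 10 | 1.32 | 30% | 0.88 | 1.04 |
| 50% | 18 | 0.96 | 51% | 0.65 | 0.94 |
| 75% | 26 | 0.79 | 67% | 0.54 | 1.07 |
| All | 35 | 0.68 | 80% | 0.47 | n/a |

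**5. Balance**

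With allocation that ignores FN, and ignoring the small blocks, the hypergeometric chance that one arm holds at least twice as many FN patients as the other is 8-16% at a 20% share and 5-9% at 30%. At 50% it is below 0.5%.

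**The case against.** The strongest reply is that only one summary sentence is loose. Hypothesis 3a carries the primary outcome, names neither females nor FN, and matches the sample and the model. In the Aim 3 sentence the closing phrase could be read as attached to the mechanistic half only, which fits the female-only imaging sub-study. Enrolling broadly and then phenotyping is a legitimate design. CART is to be used to look for interactions, and regression trees will use baseline values.

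Much of this stands. The primary comparison is sound for 3a, and 3a needs no change. The alternative reading of the Aim 3 sentence does not dispose of the point, because vagal tone is in that mechanistic half and is analysed in all nausea subjects. The tree analyses are exploratory and do not name FN.

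A reader might infer three stronger things that the documents do not support:

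- *The trial tests a different population from the one it names.* Every nausea patient must meet Rome IV functional nausea, and the randomised sample contains the FN group. It is broader, not different.
- *FN may be as rare as 10%.* That gives 8-10 FN patients in all, too few for the 15 FN females to be scanned.
- *A null result could be blamed on non-FN patients, to whom the mechanism does not apply.* The background and anticipated-benefits sections rest on vagal pathways in nausea and vomiting generally, not in FN alone.

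**Conclusion.** The mismatch is real but limited. The active-versus-sham comparison answers Hypothesis 3a in all eligible Rome IV functional-nausea adolescents. It provides no estimate for FN, so neither the nausea claim in the Aim 3 sentence nor the FN vagal-tone hypothesis is addressed as written.

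The size depends on the FN share, which is not stated. At the floor implied by the imaging sub-study there would be about 7 evaluable FN patients per arm against ~35 overall, with a confidence interval of roughly ±1 SD. Even at 50% it would be about ±0.65 SD. An FN estimate can therefore support interpretation but not confirm an effect. These figures assume that the 15 scanned patients come from the randomised cohort, equal splits between arms, and 12% dropout regardless of FN status.

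**What to change.** 1. Reword Aim 3 so that the nausea claim covers all randomised Rome IV functional-nausea adolescents and female FN attaches only to the connectivity sub-study. Leave 3a as it is. State that ~40 and ~35 per arm refer to all randomised nausea patients.
2. Include FN status, by the section D definition and classified from the Pre visit and Visits 1 and 2, as a baseline factor in the primary model. Prespecify a treatment-by-FN estimate with its confidence interval for the Nausea Severity Scale and for the vagal-tone outcome, labelled supportive.
3. Either run the 3b vagal-tone analysis in FN patients or reword 3b to nausea patients. If it is run in FN, base it on active versus sham: patients selected for low RMSSD tend to drift back towards the mean, so change from baseline alone would mislead.
4. Limit any FN-specific conclusion to these estimates.

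The cost is some rewording and added model terms from data already scheduled before the first device, with no new patients or visits. The headline claim becomes broader and the FN estimate is openly imprecise. The change should be made before unblinding.
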